#### 7.1.2 Approaches to the Analysis

The following 2 approaches will be used for the analyses:

- **Intention-to-Treat** All patients with a post-treatment endpoint measurement will be included. This will be considered the primary analysis and performed for all endpoints.
- **Per Protocol** This will be performed as a secondary analysis for the primary endpoint only. A patient who is identified as a major protocol violator will not be included. Protocol violators will be considered as follows: 1) Realize that patient did not meet Inclusion Criteria after enrolled into study; 2) Find an Exclusion criteria after enrolled into the study; 3) Regimen was

permanently stopped before 4 weeks; 4) Exacerbation requiring greater than 2 weeks of prednisone escalation. Major protocol violators will also be defined based on criteria that will be identified prior to unblinding the database.

**7.1.3 Multiplicity:** Since there is only 1 primary comparison for 1 primary endpoint for each study aim, and other comparisons are secondary and supportive, no multiplicity adjustment will be applied.

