### 3.2 Secondary Endpoints:

- Change in FEV1
- Radiographic improvement in sarcoidosis lung disease by frontal chest x-ray. Local investigators will score chest x-rays. This analysis correlates roentgenographic findings with physiologic parameters.
- Change in 6 minute walk distance, oxygen saturation and level of dyspnea.
- Change in the Saint George's Respiratory Questionnaire (SGRQ; King's Sarcoidosis Questionnaire (KSQ) for the assessment of health status; The Fatigue Assessment Scale (FAS).
- Necessity of escalating immunosuppressive therapy secondary to continued clinical deterioration, after study enrollment.
- Safety profile of regimen as evidenced by adverse events and abnormal lab values, tolerability and toxicity of the treatment regimen including comparison of reported adverse events and abnormal laboratory values compared to placebo.
- Increase in T cell biologic function through normalization of p56Lck and IL-2 expression.
- Decrease in peripheral and pulmonary T cell responses against ESAT-6 at 16 weeks compared to baseline.

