### 5.1 Blinding and Randomization

Participants will be randomized to either CLEAR therapy or placebo at a ratio of 1 to 1 stratifying by site and use of prednisone  $\geq 10$  mg or not and using a permuted-block randomization algorithm with random block sizes. Randomization schedules will be generated by a statistician who is not involved with the conduct of the clinical trial. The Vanderbilt Investigational Pharmacy will provide each site with the study drugs and site-specific treatment assignments. The placebos and colored capsules will be obtained by each site. Pills of identical appearance containing antibiotics (each a different color) or placebo will be prepared and dispensed by each site's study pharmacy. A participant's treatment assignment will only be revealed outside the pharmacy if a clinical emergency necessitates unblinding their treatment or if requested by the DSMB. Neither participants, clinical providers, nor those influencing recruitment decisions or interpretation of data will be aware of the treatment that is assigned or the order that treatments will be allocated.

Patients will be considered enrolled upon randomization. Patients receiving any amount of study drug will be considered treated. Patients discontinued from receipt of study drug for any reason, will continue to follow all other protocol requirements for the entire 180 day study period to the extent that the informed consent is still active.

Only the investigational pharmacists and the DSMB will be unblinded to randomization assignments. There are safety issues associated the CLEAR regimen; for example, levaquin and prolongation of the QT interval. If there is a significant safety issue thought related to study drug, all four study drugs within the regimen should be stopped and the patient followed until stabilization or resolution of this issue. Efforts will be made to unblind only individuals not associated with the research and who need to know, such as an attending physician. Should un-blinding of an individual become necessary during the study, the investigator at the clinical site should contact the Vanderbilt Clinical Coordinating Center (CCC) for approval and specific unblinding instructions.

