#### 7.1.4 Analysis of Secondary Endpoints

For continuous secondary endpoints, statistical analyses will be conducted using the same methods as described for the primary endpoint. For binary endpoints such as >10% improvement on FVC, the Pearson chi-square test or Fisher's exact test will be used to assess them between the two arms. If imbalance on certain important covariates which might impact these binary endpoints is observed between the treatment arms, logistic regression to control for these covariates may be conducted. The safety endpoint such as death, AE, SAE, drug-related AE, drug-related SAE, abnormal lab values, tolerability and toxicity of the treatment regimen, will be summarized (count and percent) by treatment arms and for the entire study sample. Between CLEAR and placebo comparison on these endpoints will be made using the Pearson chi-square test or Fisher's exact test.

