## 7.2 Randomization

Participants will be randomized to either CLEAR therapy or placebo at a ratio of 1 to 1 stratifying by site and use of prednisone  $\geq 10$  mg or not and using a permuted-block randomization algorithm with random block sizes. Treatment assignments of the study will be made using separate randomization schedules for each of the three participating sites. The randomization schedule will be prepared by the DCC prior to initiation of patient recruitment. Randomization schedules will be generated by a statistician who is not involved with the conduct of the clinical trial. All randomization schedules will be generated using R, will remain confidential and known only by the site pharmacists until the database is locked and randomization assignments no longer must be blinded. Randomization marks the patient's official entry into the Study. Once a participant has been started on the assigned study treatment, efforts will be made to conduct all evaluations irrespective of whether the participants complete the study treatment regimen or not, or how well the participants complies with the study treatment regimen. These efforts should continue until termination of the study. Data collections will continue even if medication must be stopped.

For the intention to treat analysis, participants will be considered treated when the first study drug is taken, regardless of the amount of study drug they receive. Participants discontinued from receipt of

study drug for any reason, will continue to follow all other protocol requirements for the entire study period to the extent that the informed consent is still active.

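### The set called intention-to-treat requires a post-treatment measurement and is applied to all endpoints, so some treated patients can be left out of the safety comparison; no safety set is defined

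*Combined protocol and SAP*

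**What the plan says.** Section 7.1.2 of the combined protocol and SAP offers two analysis approaches. The per-protocol approach is for the primary endpoint only. The other is called intention-to-treat. Its membership rule and its scope are given together: "All patients with a post-treatment endpoint measurement will be included. This will be considered the primary analysis and performed for all endpoints". The plan does not define what an endpoint measurement is.

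Safety is one of those endpoints. Section 3.2 lists "Safety profile of regimen as evidenced by adverse events and abnormal lab values, tolerability and toxicity of the treatment regimen". Section 7.1.4 (Analysis of Secondary Endpoints) says that deaths, AEs, SAEs, drug-related events, laboratory abnormalities and tolerability "will be summarized (count and percent) by treatment arms and for the entire study sample", and then: "Between CLEAR and placebo comparison on these endpoints will be made using the Pearson chi-square test or Fisher's exact test". It names no population or denominator. Section 7.4 uses the methods specified for the safety endpoints in the interim safety analysis.

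Two other places use a first-dose rule. Section 5.1 says "Patients receiving any amount of study drug will be considered treated". Section 7.2, in a sentence that opens by saying it is for the intention-to-treat analysis, says "participants will be considered treated when the first study drug is taken, regardless of the amount of study drug they receive".

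**The concern.** Safety analyses normally count everyone exposed. Here the only set with a stated scope covering safety is conditional on something that happens after exposure. The first scheduled post-dose visit is week 4, plus or minus 7 days (section 6.4, Appendix A). A patient who takes study drug and then dies, withdraws consent or is lost before that visit may have no post-treatment measurement, and section 7.1.2 then leaves that patient out.

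If such patients have more AEs than those who stay, the AE rate in their arm is understated. If there are more of them on CLEAR than on placebo, the difference between arms shrinks. Safety is part of the primary objective (section 2.1), and the interim safety analysis would inherit the same ambiguity.

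A looser reading does not settle the matter. If an AE record counts as the measurement, an early leaver with an event can enter the set while one without an event may not. Membership could then depend on the outcome being compared.

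**Working it through.** **Plan figures.** Section 7.3: SD 7.7, difference 5 points, 90% power, 20% dropout, 51 completers and 64 enrolled per arm. A two-sample t-test at two-sided 0.05 needs 50.8, so 51 per arm; 51 / (1 − 0.20) = 63.75, so 64. Both figures reproduce. The alpha level is inferred, because section 7.3 does not state it. The point here does not affect the sample size.

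**The rules side by side.**

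| Section | Who is in | Applies to |
|---|---|---|
| 7.1.2 | Patients with a post-treatment endpoint measurement | All endpoints |
| 7.2 | Counted as treated from the first dose | Intention-to-treat analysis |
| 5.1 | Counted as treated after any amount of drug | No analysis named |
| 7.1.4 (Secondary Endpoints) | Not stated | Safety endpoints |

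A treated patient with no post-dose measurement is out under 7.1.2. The wording of 7.2 points the other way. Nothing says which rule sets the safety denominator.

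**Size under the strict reading of 7.1.2.** Let m of 64 CLEAR patients be unmeasured, with AE rate p, and let the others have AE rate 0.20. Both rates and m are assumptions.

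- Reported rate: 20%.
- Rate in all treated: (0.20 × (64 − m) + p × m) / 64.
- Understatement: m × (p − 0.20) / 64.

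| m | p = 0.4 | p = 0.6 | p = 0.8 |
|---|---|---|---|
| 3 (5% of the arm) | 0.9 points | 1.9 | 2.8 |
| 6 (9%) | 1.9 | 3.8 | 5.6 |
| 13 (20%) | 4.1 | 8.1 | 12.2 |

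The last row takes 64 × 0.20 = 12.8, rounded to 13, and places the entire study dropout before any measurement.

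**Size if an AE record counts as the measurement.** Suppose early leavers with an event enter and those without do not. The numerator is then complete but the denominator is 64 − m + p × m. For m = 6 and p = 0.4: (11.6 + 2.4) / (58 + 2.4) = 14.0 / 60.4 = 23.2%, against 14.0 / 64 = 21.9%. The rate is now overstated, by 1.3 points. The direction of the error therefore depends on a definition that the plan does not give.

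**Effect on the comparison (Fisher's exact test, assumed counts).** Start from 19/64 (CLEAR) versus 6/64 (placebo), p = 0.007, and leave out CLEAR patients who had an AE, with no loss on placebo:

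| CLEAR patients left out | CLEAR | Placebo | p |
|---|---|---|---|
| 2 | 17/62 | 6/64 | 0.011 |
| 4 | 15/60 | 6/64 | 0.030 |
| 6 | 13/58 | 6/64 | 0.078 |

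From 13/64 versus 3/64 (p = 0.014), leaving out 4 gives 9/60, p = 0.070. From 26/64 versus 13/64 (p = 0.021), leaving out 4 gives 22/60, p = 0.048, and leaving out 6 gives 20/58, p = 0.10. In these scenarios two omissions leave the signal visible, while four to six can hide it.

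**The case against.** The strongest reply is that section 7.2 already attaches intention-to-treat to the first dose, so the any-dose principle is in the plan. It also notes that the safety text in 7.1.4 imposes no measurement requirement of its own. This stands in part: the defect is two unreconciled statements, not an unambiguous decision to exclude treated patients. But 7.2 says only who counts as treated. It does not say that all treated patients form the safety denominator, and 7.1.2 explicitly covers all endpoints. The reference in 7.1.4 to the whole study sample reads as a pooled column beside the two arms, not as a population definition.

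The second reply is that stopping drug is not leaving the study, and this largely stands:

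- Follow-up continues while consent is active (5.1, 7.2), and visits continue after a stop point (12.1).
- A confirmed stop point, which includes intolerable toxicity, calls for laboratory tests and spirometry (12.2).
- Patients who elect to stop are asked for at least spirometry (5.7).
- Medical discontinuations are followed to stabilization or reversal (5.6, 5.7).

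These provisions limit the exposed group to patients who die, withdraw consent or are lost with none of these measurements obtained.

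The third reply concerns the AE-record reading. AEs are ascertained from enrollment (section 11), so having no event by last contact is arguably also an observation. That is a reasonable reading, but the plan does not state it.

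A reader might infer that the rule strips toxicity events selectively from CLEAR and biases the AE rate by 4 to 12 points. The documents do not support that. Section 7.3 gives 20% as dropout over the whole study, not loss before week 4. It attributes most Phase I withdrawals to patients with advanced disease, and no document gives early-loss or AE rates by arm. Placebo leavers fall under the same rule. An extreme illustration such as 18/64 versus 6/64 (p = 0.012) turning into 10/51 versus 5/56 (p = 0.16) needs 13 versus 8 unmeasured patients, with events in 8 of 13 and 1 of 8. All of that is assumed. Leaving out two CLEAR patients with events from the same start gives 16/62 versus 6/64, p = 0.019.

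Nor is real-time safety oversight lost. SAEs go to the DSMB whatever the analysis set (7.6.4), serious, unexpected and study-related events go on a short clock (11.2), and interim p-values are not formal inference (7.4).

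**Conclusion.** Wrong as written, as an analysis-set rule. Followed literally, section 7.1.2 can remove exposed patients from the safety comparison. It conflicts with the first-dose wording in 7.2, and no safety set resolves the conflict. The text shows that such patients can be left out, not that they must be.

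The size is uncertain and probably modest: about 1 to 3 points of understatement in the CLEAR AE rate if 3 of 64 patients are unmeasured, and 2 to 6 points if 6 are. The range of 4 to 12 points is a worst case, not an estimate. These figures rest on assumed AE rates of 20% in patients who stay and 40% to 80% in early leavers, and on the strict reading of the rule. Greater early loss on CLEAR than on placebo is plausible but not documented. No stated figure in the plan is wrong.

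**What to change.** In the combined protocol and SAP:

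1. Add a safety set to 7.1.2: all randomized patients who took at least one dose of any study drug, with no requirement for a post-treatment measurement.
2. State in 7.1.4 (Analysis of Secondary Endpoints) that this set is the denominator for deaths, AEs, SAEs and tolerability, and in 7.4 that the interim safety analysis uses it. Restrict only laboratory summaries to patients with a post-dose sample, and report that number by arm.
3. Limit the measurement-based set in 7.1.2 to efficacy endpoints, and reconcile its wording with the first-dose sentence in 7.2.

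The cost is a few sentences. AEs are already collected from enrollment (section 11). Visits, sample size and patient management stay as they are. The change should be made before unblinding.

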#### 7.1.4 Analysis of Secondary Endpoints

For continuous secondary endpoints, statistical analyses will be conducted using the same methods as described for the primary endpoint. For binary endpoints such as >10% improvement on FVC, the Pearson chi-square test or Fisher's exact test will be used to assess them between the two arms. If imbalance on certain important covariates which might impact these binary endpoints is observed between the treatment arms, logistic regression to control for these covariates may be conducted. The safety endpoint such as death, AE, SAE, drug-related AE, drug-related SAE, abnormal lab values, tolerability and toxicity of the treatment regimen, will be summarized (count and percent) by treatment arms and for the entire study sample. Between CLEAR and placebo comparison on these endpoints will be made using the Pearson chi-square test or Fisher's exact test.

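### Binary endpoints get an unstratified test, with adjustment optional and triggered by observed imbalance, so the site and prednisone strata used in randomization are not carried into the analysis

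*Combined protocol and SAP*

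**What the plan says.** Sections 5.1 and 7.2 both describe stratified permuted-block randomization: patients are "randomized to either CLEAR therapy or placebo at a ratio of 1 to 1 stratifying by site and use of prednisone", with the prednisone factor cut at 10 mg. Section 7.2 adds "separate randomization schedules for each of the three participating sites", which makes 3 × 2 = 6 strata.

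For binary efficacy endpoints, Section 7.1.4 (Analysis of Secondary Endpoints) says: "For binary endpoints such as >10% improvement on FVC, the Pearson chi-square test or Fisher's exact test will be used". No strata are mentioned. Adjustment is conditional, "If imbalance on certain important covariates which might impact these binary endpoints is observed between the treatment arms", and even then optional: "logistic regression to control for these covariates may be conducted". Binary safety endpoints get the same two tests, with no provision for adjustment: "Between CLEAR and placebo comparison on these endpoints will be made using the Pearson chi-square test or Fisher's exact test".

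No test or model in Section 7 names site or prednisone. The primary t-test or Wilcoxon test in Section 7.1.1 is also unstratified. The exploratory mixed model there mentions only covariates such as age, race and gender. Section 7.1.3 calls all comparisons other than the primary one secondary and supportive. No power or response rate is given for any binary endpoint.

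**The concern.** There are two separate issues.

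First, the adjustment rule is not prespecified. The plan does not say which covariates count, how large an imbalance must be, whether adjustment then becomes obligatory, or whether the adjusted result replaces or supplements the chi-square result. One endpoint could therefore have several defensible answers, selected after the data are seen. This needs no assumption about prognosis.

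Second, observed imbalance is the wrong criterion. What makes adjustment useful is that a factor predicts the outcome. Blocking within strata balances site and prednisone by design, so the trigger will rarely pick them up even if they predict strongly. Baseline prednisone is a plausible predictor of the need to escalate immunosuppression, a secondary endpoint in Section 3.2. That is an inference, although the choice to stratify on prednisone points the same way. If the strata are prognostic, a test that ignores them overstates the variance of the treatment difference, which makes it conservative and can cost power.

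**Working it through.** **The plan's own figure.** Section 7.3 gives SD 7.7, difference 5, power 90% and 51 completers per arm. Alpha is not stated; two-sided 0.05 is assumed. Normal approximation: n = 2(1.960 + 1.282)² × 7.7² / 5² = 49.8, so 50; the t distribution gives 50.8, so 51. With 20% dropout, 51 / 0.80 = 63.75, so 64. The figure reproduces. It concerns the continuous primary endpoint and is used below only to fix 51 per arm.

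**Effect on type I error (closed form).** Assume two equal strata, balanced by blocking, with event rates p₁ and p₂ and mean p. The Pearson test uses variance V = p(1−p). The variance that applies after stratified randomization is W, the mean of pₛ(1−pₛ). Actual two-sided type I error = 2[1 − Φ(1.96 √(V/W))]. Set p = 1/3, so V = 0.2222, and choose p₁, p₂ to give the stated stratum log odds ratio (LOR).

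| Stratum LOR (odds ratio) | p₁, p₂ | W | V/W | 1.96√(V/W) | Type I error |
|---|---|---|---|---|---|
| 1.0 (2.7) | 22.5%, 44.1% | 0.2105 | 1.055 | 2.01 | 4.4% |
| 2.0 (7.4) | 13.4%, 53.3% | 0.1824 | 1.218 | 2.16 | about 3.0% |
| 2.5 (12.2) | 9.8%, 56.9% | 0.1667 | 1.333 | 2.26 | 2.4% |

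**Effect on power (simulation).** Same strata, 51 per arm, average control rate one third, treatment LOR 1.1 within each stratum, Pearson against Mantel-Haenszel:

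- LOR 0 to 1.0: no material difference.
- LOR 2.0: 62% unstratified, 68% stratified (6 points).
- LOR 2.5: 51% unstratified, 62% stratified (11 points).

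Other simulation set-ups with the same sample size and treatment effect gave losses of 5 to 9 points at 2.0 and 11 to 16 at 2.5.

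**A check tied to the plan's own endpoint.** Read the FVC responder threshold as more than 10 absolute points and assume normal changes with means 5 and 0 and SD 7.7. Responder rates are then 1 − Φ(5/7.7) = 25.8% and 1 − Φ(10/7.7) = 9.7%. Simulation used 102 patients, six strata (three equal sites by prednisone, half in each prednisone stratum) and assumed block sizes of 2 and 4. Prednisone and site each shift the log odds by up to ±s, so the LOR between the extremes of each factor is 2s.

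| s | Unstratified power | Cochran-Mantel-Haenszel power |
|---|---|---|
| 0 | 58.5% | 58.2% |
| 0.25 | 58.8% | 59.0% |
| 0.5 | 58.5% | 60.2% |
| 1.0 | 57.8% | 64.7% |

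At s = 1.0 the unstratified type I error was 3.9% here, and 3.1% to 3.5% for the other pairs of rates tried.

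**Cost of stratifying when it does not help.** With six sites (12 strata) and s = 0, power was 58.8% unstratified and 57.7% stratified, a cost of about 1 point.

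**Sparseness.** At these responder rates, 51 × 0.258 + 51 × 0.097 = 18 events are expected, or about 3 per stratum over six strata.

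**The case against.** The strongest reply is that nothing in the documents says site or prednisone predicts any binary endpoint. The losses of 6 and 11 points need stratum odds ratios of 7.4 and 12.2, which are large. At an odds ratio of 2.7 the difference is negligible. This stands: a reader might infer that the plan loses power as a matter of fact, but the documents support only that it can.

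A reader might also infer that the unstratified p-values are wrong or the false-positive rate inflated. The calculation shows the opposite direction: the prespecified test on its own is conservative and remains valid.

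Nor can one say that the trigger would never select the strata. Section 7.1.2 analyses patients with a post-treatment measurement, and Section 7.3 allows for 20% dropout. Blocking balances those randomized, not necessarily those analysed, so 'rarely' is the defensible word.

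The regression can be read as a supplement to the chi-square test, and the endpoints are supportive in a Phase II study. That limits the consequence, but the plan does not state the precedence, so the room for choice remains.

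Finally, adjusting for everything by logistic regression could do harm. Treatment, prednisone, two site terms and baseline FVC make five parameters for about 18 events, or 3.6 events each. This stands, and it bears on which remedy to choose.

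**Conclusion.** The point holds as a free improvement. The analysis of binary endpoints does not follow the stratified randomization, and its adjustment rule is optional, data-triggered and unspecified.

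The size depends on assumptions that the documents cannot settle: about nil for weakly or moderately prognostic strata, and roughly 6 to 11 points of power in the two-stratum setting if the strata are very strongly prognostic, with type I error then falling to about 3.0% and 2.4%. In the six-stratum check on the FVC responder endpoint the largest gain was 64.7 − 57.8 = 6.9 points. No size can be put on the freedom to choose covariates, because the plan names neither covariates nor threshold.

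A reader might take this as an error in the sample size. It is not: 51 and 64 per arm reproduce, and no power is claimed for any binary endpoint. The primary test in Section 7.1.1 omits the same strata, and the omission matters more there.

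**What to change.** In Section 7.1.4 (Analysis of Secondary Endpoints):

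- Name one main test for every binary efficacy endpoint: a Cochran-Mantel-Haenszel test stratified by prednisone (10 mg or more, or not) and site.
- State a rule, fixed before unblinding, for pooling small sites or sparse strata.
- Delete the imbalance trigger and the optional logistic regression attached to it.
- Keep the unstratified chi-square or Fisher test as a sensitivity analysis, and Fisher's test for sparse safety events.
- Word the prednisone stratum the same way throughout; the synopsis omits the 10 mg cut-off given in Sections 5.1 and 7.2.

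The cost is wording only, since the stratum variables are recorded at randomization. The downside is up to about 1 point of power if the strata are numerous and not prognostic.

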## 2. Objectives

### 2.1 Primary Objective

To assess the efficacy and safety of oral CLEAR therapy in patients with confirmed progressive pulmonary sarcoidosis.

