### 7.3 Sample Size Justification

Sample size is calculated for primary endpoint; change from baseline of FVC percent predicted. Using data from 34 participants treated with Bosentan to treat pulmonary hypertension, we obtained the SD of 7.7 for the primary endpoint. We need a sample size of 51 completed participants per arm to have 90% power to detect a 5% difference (5% in CLEAR vs. 0% in placebo) in change of FVC percent predicted from baseline. To factor in a 20% dropout rate, we plan to enroll 64 subjects per arm. This brings the sample size to 128 participants. In the Phase I trial, we experienced a higher drop rate 30%, but review of the clinical data demonstrates that patients with advanced disease accounted for the majority of the study withdrawals. The Phase II trial will allow patients to drop one study drug, and will include a research nurse coordinator to encourage study participation. We anticipate that we will have not have as high a study withdrawal rate.

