### 7.4 Interim Monitoring

The DSMB will receive a report of adverse events (blinded by arm) after 15 participants have completed study treatment to review. This review will be conducted by the chair of the DSMB, who will recommend either that the study continue or that there be a review of the first 15 participant's data by the DSMB committee. An interim safety analysis will also be performed after 50 participants complete study drug treatment. This interim analysis will be presented to the DSMB by the PI and the study statistician or his/her designee. The results will be blinded and presented on a coded study arm basis (i.e. A and B arm) unless the DSMB votes to receive unblinded data. The interim analysis will focus on the safety profile of the study treatments. These analyses will be conducted based on the methods specified in the Data Analysis Plan for the safety endpoints. Since the interim analysis is not designed to draw formal inference on these safety endpoints, the magnitude of the between-treatment differences and the p-values will be provided solely to help the DSMB to evaluate the safety profile. Although efficacy data will also be presented, no early stopping of the trial based on the efficacy endpoints is planned for this Phase II study, because it is unlikely that an efficacy study of less than 128 subjects will have credibility with the scientific community. The DSMB is further described in Section Data Safety Monitoring Board Charter and Plan.

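### Between-arm safety analysis rests on chi-square or Fisher tests without intervals, so for low-incidence harms it cannot show how much excess risk remains open

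*Combined protocol and SAP*

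**What the plan says.** Section 2.1 gives one primary objective, covering both efficacy and safety: "To assess the efficacy and safety of oral CLEAR therapy in patients with confirmed progressive pulmonary sarcoidosis". Section 3.2 then places safety among the secondary endpoints: "Safety profile of regimen as evidenced by adverse events and abnormal lab values".

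Section 7.1.4 (Analysis of Secondary Endpoints) lists the safety endpoints: death, AEs, SAEs, drug-related AEs and SAEs, abnormal laboratory values, tolerability and toxicity. These "will be summarized (count and percent) by treatment arms and for the entire study sample". The comparison follows: "Between CLEAR and placebo comparison on these endpoints will be made using the Pearson chi-square test or Fisher's exact test". No rule is given for choosing between the two tests, and no interval, bound or margin is named.

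The sample size in Section 7.3 is derived for change in FVC percent predicted only. Allocation is equal (Section 7.2), and "To factor in a 20% dropout rate, we plan to enroll 64 subjects per arm". No precision or power figure is given for any safety endpoint. Section 7.1.3 says that "no multiplicity adjustment will be applied".

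For the interim look in Section 7.4, "the magnitude of the between-treatment differences and the p-values will be provided solely to help the DSMB to evaluate the safety profile". That section also states that formal inference on safety is not intended at that point. The final analysis carries no comparable statement.

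**The concern.** The trial intends to draw a conclusion on safety for a four-drug regimen, with a sample sized for a lung-function endpoint. Counts and percents by arm estimate the difference but carry no measure of precision, and the only inferential quantity planned is a p-value for each endpoint.

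For events that occur in a small share of participants, a non-significant result is likely at this size whether or not CLEAR increases the risk. The trial's readers need to know how large an excess remains compatible with the data. A test does not answer that; an interval does. The matter is most relevant to deaths, SAEs and individual uncommon toxicities, which are plausibly the low-incidence categories here (an assumption, since no expected rates are given).

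**Working it through.** **Inputs from the documents.** 64 randomized and 51 completers per arm, difference 5 points, SD 7.7, power 90%, dropout 20% (Section 7.3); 1:1 allocation (Section 7.2).

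**Assumed.** Two-sided 0.05 and placebo event rates from 2% to 30%. The documents give neither.

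**Step 1: reproduce the plan's own figure.** For a two-sample t-test with n = 51 per arm, the noncentrality is 5 / (7.7 × √(2/51)). At two-sided 0.05 this gives power 0.901 (0.895 at n = 50), so 51 per arm is right. One-sided 0.05 would need only 41, which supports the two-sided assumption. Dropout: 51 / (1 − 0.20) = 63.75, rounded up to 64. The figure is correct, but it concerns FVC only.

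**Step 2: power of the planned safety tests.** With X and Y independent binomial counts on CLEAR and placebo, power is the sum of P(X = x) × P(Y = y) over all pairs with x > y and p ≤ 0.05. Chi-square is without continuity correction. Results in percent, Fisher / chi-square:

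| Placebo → CLEAR | 64 per arm | 51 per arm |
|---|---|---|
| Doubling: 2% → 4% | 1.3 / 7.5 | 0.6 / 5.4 |
| 5% → 10% | 9.8 / 18.5 | 6.5 / 14.5 |
| 10% → 20% | 27.0 / 34.7 | 20.1 / 28.5 |
| 15% → 30% | 45.2 / 53.3 | 36.4 / 44.8 |
| 20% → 40% | 63.0 / 70.7 | 52.7 / 60.6 |
| 30% → 60% | 90.8 / 93.3 | 84.2 / 88.6 |
| Tripling: 2% → 6% | 6.5 / 18.9 | 3.4 / 14.5 |
| 5% → 15% | 35.9 / 48.6 | 25.2 / 39.3 |
| 8% → 24% | 63.0 / 70.9 | 50.3 / 60.7 |
| 10% → 30% | 76.7 / 82.5 | 65.3 / 73.4 |
| 15% → 45% | 95.2 / 97.0 | 89.5 / 92.8 |

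The 51 column is shown because Section 7.1.2 restricts the analysis of all endpoints to patients with a post-treatment measurement, so the safety denominator could lie between 51 and 64.

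At 64 per arm, power for a doubling stays below one half up to a placebo rate of about 10% with chi-square and about 15% with Fisher. For a tripling it stays below one half up to about 5% with either test (only just, with chi-square: 48.6%). Above these rates the tests detect the change more often than not.

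**Step 3: what an interval would add.** Newcombe's 95% interval for p₁ − p₂ uses the Wilson limits (l, u) of each arm: lower = (p₁ − p₂) − √[(p₁ − l₁)² + (u₂ − p₂)²]; upper = (p₁ − p₂) + √[(u₁ − p₁)² + (p₂ − l₂)²].

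Example, 5/64 on CLEAR and 1/64 on placebo: p₁ = 7.81%, Wilson 3.38% to 17.02%; p₂ = 1.56%, Wilson 0.28% to 8.33%. Difference = 6.25 points.
- Lower = 6.25 − √(4.43² + 6.77²) = −1.8.
- Upper = 6.25 + √(9.21² + 1.28²) = +15.5.

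| CLEAR v placebo, of 64 each | Fisher p | Difference, points (95% interval) |
|---|---|---|
| 5 v 5 | 1.00 | 0.0 (−10.2 to 10.2) |
| 6 v 3 | 0.49 | 4.7 (−4.9 to 14.8) |
| 5 v 1 | 0.21 | 6.3 (−1.8 to 15.5) |
| 9 v 3 | 0.13 | 9.4 (−1.1 to 20.4) |

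For zero events, the exact upper limit of the two-sided 95% interval is 1 − 0.025^(1/n): 5.6% at n = 64 and 7.0% at n = 51.

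**The case against.** The strongest reply is that nothing here is an error. Chi-square and Fisher tests on adverse-event tables are conventional, sizing a Phase II trial on efficacy alone is ordinary, and Section 7.1.3 treats comparisons other than the primary one as supportive. Counts and percents by arm are planned, so a reader can see the difference and compute an interval. Safety oversight also draws on investigators' judgement of relatedness and on DSMB review. All of this stands. It limits the point to an improvement in method and reporting.

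Two stronger readings are tempting, and the documents support neither. A reader might infer that a doubling or tripling of any adverse-event rate would usually be non-significant. That depends on placebo rates that are not given, and it fails for common events: 20% to 40% is detected with 63% (Fisher) or 71% (chi-square) power, and 10% to 30% with 77% or 83%. The choice of test can matter too: 5 events against 0 gives p = 0.058 by Fisher but 0.023 by chi-square.

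A reader might also infer that the plan treats non-significance as proof of safety. No section says so, and no significance threshold or decision rule for safety is stated. At the interim, Section 7.4 disclaims formal inference and already gives the DSMB the size of the differences.

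What remains is that the estimates planned have no stated precision, so they do not bound the excess harm.

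**Conclusion.** The point holds for low-incidence harms. At 64 per arm and two-sided 0.05, a doubling is usually missed at placebo rates of about 10% or lower (about 15% with Fisher), and a tripling at about 5% or lower. With fewer analysed participants the tests detect less. Larger changes in common events are usually detected. These statements rest on an assumed significance level and assumed placebo rates; that SAEs, deaths and single uncommon toxicities fall in the low range is also an assumption.

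The planned tests are acceptable as description. They are a weak basis for the safety part of the primary objective, because they cannot say how much excess risk has been excluded. A cheap and better method is available, so the change is worth making. It does not affect the sample size, which is correctly derived for FVC.

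**What to change.** In Section 7.1.4 (Analysis of Secondary Endpoints):
- Make the risk difference, CLEAR minus placebo, with a 95% confidence interval (Newcombe or exact) the main between-arm result for the safety endpoints.
- Where the CLEAR count is zero, report the exact upper limit of the event rate.
- Keep the chi-square or Fisher p-values as descriptive.
- State that safety conclusions will quote the upper end of the interval and will not rest on non-significance.

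Optionally, in Section 7.4, show the same intervals beside the difference magnitudes already planned for the DSMB.

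The cost is SAP wording and table shells; sample size, visits and data collection are unchanged. The downside is that the intervals will be wide for uncommon events, so the safety statement will be more cautious.
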